LIST OF ABBREVIATIONS

Abbreviations pertain to the statistical analysis plan (SAP) only (not the tables, figures, and listings [TFLs]).

ADaM	Analysis Data Model
AE	adverse event
ANOVA	analysis of variance
AUC _{inf}	area under the plasma concentration-time curve from time zero extrapolated to infinity
AUC _{0-tlast}	area under the plasma concentration-time curve from time zero to time of last quantifiable concentration
BLQ	below the limit of quantification
CDISC	Clinical Data Interchange Standards Consortium
CI	confidence interval
CL/F	apparent total clearance
C _{max}	maximum observed plasma concentration
COVID-19	coronavirus disease 2019
CSR	clinical study report
CTCAE	Common Terminology Criteria for Adverse Events
CV	coefficient of variation
DMP	data management plan
ECG	electrocardiogram
eCRF	electronic case report form
GLSM	geometric least squares mean
ICH	International Council for/Conference on Harmonisation
LLOQ	lower limit of quantification
ln	natural log
LSM	least squares mean
MedDRA	Medical Dictionary for Regulatory Activities
PK	pharmacokinetic(s)
QTcF	QT interval corrected for heart rate using Fridericia's formula
SAP	statistical analysis plan
SD	standard deviation
SDV	source document verification
t _{1/2}	apparent plasma terminal elimination half-life
TEAE	treatment-emergent adverse event
TFL	table, figure, and listing
t _{lag}	absorption lag time
t _{max}	time of the maximum observed plasma concentration
V _{z/F}	apparent volume of distribution during the terminal phase
WHODrug	World Health Organization Drug Dictionary

λ_z apparent terminal elimination rate constant

1. INTRODUCTION

This SAP has been developed after review of the clinical study protocol (Final Protocol dated 18 May 2022) and electronic case report form (eCRF).

This SAP describes the planned analysis of the pharmacokinetic (PK), safety, and tolerability data from this study. A detailed description of the planned TFLs to be presented in the clinical study report (CSR) is provided in the accompanying TFL shells document.

In general, the analyses are based on information from the protocol, unless they have been modified by agreement with Amgen Inc. A limited amount of information about this study (eg, objectives, study design) is given to help the reader's interpretation.

This SAP must be finalized prior to the first subject enrollment (the point of enrollment occurs at the time of subject number allocation). Additionally, the SAP and TFL shells should be finalized prior to any programming activities commencing.

This SAP supersedes any statistical considerations identified in the protocol; where considerations are substantially different, they will be so identified. If additional analyses are required to supplement the planned analyses described in this SAP, they may be performed and will be identified accordingly in the CSR. Any substantial deviations from this SAP will be agreed with Amgen Inc. and identified in the CSR.

This SAP is written with consideration of the recommendations outlined in the International Conference on Harmonisation (ICH) E3 guideline *Structure and Content of Clinical Study Reports*, ICH E8 guideline *General Considerations for Clinical Trials*, ICH E9 guideline *Statistical Principles for Clinical Trials*, and ICH E9 R1 guideline *Addendum on Estimands and Sensitivity Analysis in Clinical Trials to the Guideline on Statistical Principles for Clinical Trials*.^{1,2,3,4}

The document history is presented in [Appendix 1](#).

2. STUDY OBJECTIVES

The primary objective of the study is:

- to evaluate the effects of omeprazole (a PPI) and an acidic beverage on sotorasib PK when administered orally in healthy volunteers.

The secondary objective of the study is:

- to evaluate safety and tolerability of sotorasib when coadministered with omeprazole and an acidic beverage in healthy subjects.

3. STUDY ENDPOINTS

3.1. Primary Endpoints:

The primary endpoints of the study are sotorasib PK parameters on Days 1 and 9:

- C_{\max}
- AUC_{inf}
- area under the plasma concentration-time curve from time zero to time of last quantifiable concentration (AUC_{last})

3.2. Secondary Endpoints:

The secondary endpoints of the study are:

- adverse events
- clinical laboratory tests
- 12-lead ECGs
- vital signs.

[figure not shown]
4. STUDY DESIGN

This will be a Phase 1, single-center (United States), open-label, fixed sequence study to investigate the effect of coadministration of omeprazole with an acidic beverage on the PK of sotorasib in healthy male and healthy female subjects. Up to 14 subjects will be enrolled to ensure that 12 subjects complete the study. All subjects will receive each of the following treatments:

- Day 1: 960 mg sotorasib (8 x 120 mg tablets) administered orally with 240 mL of water after an overnight fast of at least 10 hours
- Days 4 to 8: 40 mg omeprazole (delayed release capsule) administered orally with 240 mL of water QD after an overnight fast of at least 10 hours
- Day 9: 40 mg omeprazole (delayed release capsule) followed by 960 mg sotorasib (8 x 120 mg tablets) administered orally within 5 minutes with 240 mL of an acidic beverage after an overnight fast of at least 10 hours.

An overview of the study design is shown in [Figure 1](#).

Figure 1: Study Schematic

Potential subjects will be screened to assess their eligibility to enter the study within 28 days prior to the first dose administration. Subjects will be admitted into the Clinical Research Unit (CRU) on Day -1 and be confined to the CRU until discharge/end of study (EOS) on Day 11.

The total duration of study participation for each subject (from Screening through EOS visit) is anticipated to be approximately 5.5 weeks.

The start of the study is defined as the date the first enrolled subject signs an Informed Consent Form (ICF). The point of enrollment occurs at the time of subject number allocation. The end of the study is defined as the date of the last subject's last assessment (scheduled or unscheduled).

5. SAMPLE SIZE JUSTIFICATION

Approximately 14 subjects will be enrolled in order that approximately 12 subjects complete the study. The sample size for this study was based upon precedent set by other PK studies of a similar nature and was not based on power calculations.

6. STUDY TREATMENTS

The study treatment names, abbreviations, and ordering to be used in the TFLs are presented in [Table 1](#).

Table 1: Presentation of Study Treatments in TFLs

Study Treatment	Order in TFLs
Sotorasib administered alone	1
Omeprazole coadministered with Sotorasib and an acidic beverage	2

All TFLs will be based on actual treatments (eg, if subject was assigned to receive placebo but was wrongfully dosed with active treatment they would be summarized and listed under active treatment).

7. DEFINITIONS OF POPULATIONS

Any protocol deviations, including those due to coronavirus disease 2019 (COVID-19) and related restrictions (see [Section 8.1.1](#)), will be considered prior to database lock for their importance and taken into consideration when assigning subjects to populations.

7.1. All Subjects Population

The all subjects population will include all subjects who signed the ICF and had any study assessment recorded in the database per the protocol.

7.2. Safety Population

The safety population will include all subjects who received at least 1 dose of sotorasib and have at least 1 postdose safety assessment.

7.3. Pharmacokinetic Population

The PK population will include all subjects who received at least 1 dose of sotorasib and have evaluable PK data. The PK population for the primary endpoint analysis will include all subjects who received both sotorasib, and sotorasib in combination with omeprazole and an acidic beverage, and have evaluable PK data. A subject will be excluded from the PK summary statistics and statistical analysis if the subject has an adverse event of vomiting that occurs at or before 2 times median t_{max} or diarrhea within 24 hours of dosing.

8. STATISTICAL METHODOLOGY

8.1. General

Listings will be provided for all data captured in the database, with the exception of medical history. Listings will include all subjects assigned to the all subjects population and include data up to the point of study completion or discontinuation. Subjects are generally considered to have completed the study if they complete the scheduled follow-up visit (rather than early termination visit). Any subject who discontinues the study will be identified accordingly in the listings. Summaries and statistical analyses will include the subjects assigned to the relevant population based on data type.

Data analysis will be performed using the SAS® statistical software package Version 9.4 (or higher if a new version is issued during the study).

Analysis Data Model (ADaM) datasets will be prepared using Clinical Data Interchange Standards Consortium (CDISC) ADaM Version 2.1 (or higher if a new version is issued during the study) and CDISC ADaM Implementation Guide Version 1.1 (or higher if a new version is issued during the study). Pinnacle 21 Community Validator Version 4.0.1 (or higher if a new version is issued during the study) will be utilized to ensure compliance with CDISC standards.

For all statistical analyses, the hypothesis testing will be two one-sided t-test with each side tested on 0.05 significance level, unless specifically stated otherwise.

Where reference is made to 'valid' data, this refers to non-missing data which meet the predetermined criteria (eg, are not flagged for exclusion).

Where reference is made to 'all calculations', this includes, but is not limited to, summary statistics, statistical analyses, baseline derivation, changes from baseline and percentage changes from baseline.

All figures will be produced on linear-linear or discrete-linear scales, as applicable, unless specifically stated otherwise.

8.1.1. Handling of Data Quality Issues Due to Coronavirus Disease 2019 and Related Restrictions

Due to COVID-19 and related restrictions, there is a high risk for impact to data integrity, with the recognized potential for:

- Missed visits, caused by, for example:
 - Subject unable to travel to site due to restrictions, the need to quarantine, or COVID-19 infection
 - Subject unwilling to go to site due to fear of COVID-19 infection
 - Site postponing subject's visit due to investigator not being available (eg, if they have been dispatched to hospital handling COVID19 infections)
- Site unable to replenish supply of investigational product
- Incomplete data entry by sites due to limited resources to support study or no access to source documents or to eCRF
- Outstanding source document verification (SDV) due to sponsor or country restrictions on remote SDV, or no or limited access to site(s) for on-site visits
- Unanswered queries

At the time of the reporting of the study results, all protocol deviations due to COVID-19 or related restriction will be assessed for their severity and impact on the analyses. If needed, appropriate statistical methods will be applied as a mitigating action (eg, data might be categorized into 2 analysis groups, with and without COVID-19 and related restrictions impact); however, this will exclude any imputations of the missing values. Any mitigating actions will be agreed with Amgen Inc in advance and identified in the CSR.

8.1.2. Calculation of the Summary Statistics

For continuous data the following rules will be applied:

- Missing values will not be imputed, unless specifically stated otherwise.
- Unrounded data will be used in the calculation of summary statistics.
- If the number of subjects with valid observations (n) <3, summary statistics will not be calculated, with the exception of n, minimum, and maximum.
- In general, as early termination data are not associated with any scheduled timepoint, they will be excluded from all calculations of summary statistics and statistical analyses. Exceptions may be made where justified.

For categorical data the following rules will be applied:

- For ordered categorical data (eg, adverse event [AE] severity), all categories between the possible minimum and maximum categories will be included, even if n = 0 for a given category.
- For non-ordered categorical data (eg, race), only those categories for which there is at least 1 subject represented will be included; unless specifically stated otherwise.
- Missing values will not be imputed, unless specifically stated otherwise. A ‘missing’ category will be included for any parameter for which information is missing. This will ensure that the population size totals are consistent across different parameters.

8.1.3. Repeat and Unscheduled Readings

For vital signs and 12-lead ECG data only, any predose value recorded in addition to the original value or a postdose value recorded within 15 minutes of the original value will be defined as a repeat value; any postdose value recorded more than 15 minutes after the original value will be defined as an unscheduled value. For all other data types (eg, laboratory parameters), any value recorded in addition to the original value will be defined as an unscheduled value.

The original value will be replaced by the last associated repeat value in all calculations.

As unscheduled values are not associated with any scheduled timepoint, they will be excluded from all calculations, with the exception of the baseline derivation (see [Section 8.1.4](#)) and 12-lead ECG outlier analysis (see [Section 8.6.4](#)).

8.1.4. Definitions of Baseline, Change from Baseline, and Percentage Change from Baseline

The baseline will be defined as the last value recorded prior to dosing. If the date/time of the value is incomplete or missing, it will be excluded from the baseline calculation, unless the incomplete date/time indicates the value was recorded prior to dosing.

Individual changes from baseline will be calculated by subtracting the individual subject's baseline value from the value at the postdose timepoint.

Individual percentage changes from baseline will be calculated by subtracting the individual subject's baseline value from the value at the postdose timepoint, then dividing this calculated value by the individual subject's baseline value and multiplying by 100.

The summary statistics for change from baseline and percentage changes from baseline will be derived from individual subjects' values (eg, mean change from baseline will be the mean of the individual changes from baseline for all subjects, rather than difference between the mean value at the postdose timepoint and mean value at baseline).

See [Section 8.1.3](#) for more detail on handling repeat and unscheduled readings in the calculations.

8.2. Subject Disposition and Population Assignment

Subject disposition and population assignment will be listed.

A summary table by treatment will be provided, based on the safety population.

8.3. Screening Demographics

The screening demographics including age, sex, race, ethnicity, height, body weight, and body mass index will be listed.

A summary table by treatment will be provided, based on the safety population.

8.4. Prior and Concomitant Medication

Prior medication will be defined as medication that ends prior to the first dose. Concomitant medication will be defined as medication that starts during or after the first dose or starts but does not end prior to the first dose.

Prior and concomitant medications will be coded using the World Health Organization Drug Dictionary (WHODrug) Global, Format B3, Version March 2022 (or later if a new version is

issued during the study; see the data management plan [DMP] for more details). Prior and concomitant medications will be listed.

8.5. Pharmacokinetic Assessments

8.5.1. Pharmacokinetic Analysis

The following PK parameters will be determined where possible from the plasma concentrations of sotorasib using noncompartmental methods in validated software program Phoenix WinNonlin (Certara, Version 8.1.1 or higher):

Parameter	Units ^a	Definition
AUC _{0-t_{last}}	h*ng/mL	area under the concentration-time curve from time 0 to the time of the last quantifiable concentration (t _{last}) ^b
AUC _{inf}	h*ng/mL	area under the concentration-time curve from time 0 extrapolated to infinity ^c
C _{max}	ng/mL	maximum observed concentration
t _{max}	h	time of the maximum observed concentration
t _{last}	h	time of the last quantifiable concentration
t _{1/2}	h	apparent terminal elimination half-life
CL/F	L/h	apparent total clearance
V _{z/F}	L	apparent volume of distribution during the terminal phase

^a Units are based on concentration units (provided by the bioanalytical lab or preferred units for presentation of PK parameters) and dose units used in the study.

^b The AUC will be calculated using the linear trapezoidal (linear interpolation) rule.

^c Based on the last observed quantifiable concentration

Additional PK parameters may be determined where appropriate.

Pharmacokinetic analysis will be carried out where possible using actual blood sampling times postdose. If an actual time is missing, the sample concentration result will be treated as missing unless there is scientific justification to include the result using the nominal time.

The parameters C_{max}, t_{last}, and t_{max} will be obtained directly from the concentration-time profiles. If C_{max} occurs at more than 1 timepoint, t_{max} will be assigned to the first occurrence of C_{max}.

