1.2. Pharmacokinetics

The PK of sotorasib have been characterized in healthy subjects and in subjects with *KRAS p.G12C*-mutated solid tumors, including NSCLC. Sotorasib exhibited nonlinear, time-dependent, PK over the dose range of 180 to 960 mg (0.19 to 1 times the approved recommended dosage) QD with similar systemic exposure (ie, area under the plasma concentration-time curve [AUC] from time zero to 24 hours postdose [AUC_{0-24h}] and maximum observed plasma concentration [C_{max}]) across doses at steady state. Sotorasib systemic exposure was comparable between film-coated tablets and film-coated tablets predispersed in water administered under fasted conditions. Sotorasib plasma concentrations reached steady state within 22 days. No accumulation was observed after repeat sotorasib dosages with a mean accumulation ratio of 0.56 (coefficient of variation [CV]: 59%).

Absorption

The median time of the maximum observed concentration (t_{max}) is 1 hour.

Effect of Food

When 960 mg sotorasib was administered with a high-fat, high-calorie meal (containing approximately 800 to 1000 calories with 150, 250, and 500 to 600 calories from protein, carbohydrate, and fat, respectively) in patients, sotorasib AUC_{0-24h} increased by 25% compared to administration under fasted conditions.

Distribution

The sotorasib mean apparent volume of distribution at steady state (V_{ss}) is 211 L (CV: 135%). In vitro, sotorasib plasma protein binding is 89%.

Elimination

The sotorasib mean terminal elimination half-life is 5 hours (standard deviation: 2). At 960 mg sotorasib QD, the sotorasib steady-state apparent clearance is 26.2 L/hr (CV: 76%).

Metabolism

The main metabolic pathways of sotorasib are nonenzymatic conjugation and oxidative metabolism with cytochrome P450 (CYP)3As.

Excretion

After a single dose of radiolabeled sotorasib, 74% of the dose was recovered in feces (53% unchanged) and 6% in urine (1% unchanged).

18 May 2022 Page 15 of 69

Specific Populations

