- e Vital signs measurements (oral body temperature, respiratory rate, supine blood pressure, and supine heart rate) will be carried out, prior to having blood drawn, at Screening, Check-in, predose, and at 1, 24, and 48 hours after each dose of sotorasib, and at EOS or ET. Blood pressure and heart rate will be measured using the same arm for each reading after the subject has been resting in the supine position for at least 5 minutes.
- ^fClinical chemistry (fasted at least 8 hours), hematology, and urinalysis.
- g eGFR will be calculated using the Modification of Diet in Renal Disease equation.
- ^h A full physical examination at Screening and Check-in and a symptom-directed physical examination at EOS or ET.
- ¹ Dose administration of sotorasib is to occur during the mornings of Days 1 and 9 following an overnight fast of at least 10 hours. On Day 9, sotorasib administration will occur within 5 minutes after administration of omeprazole with an acidic beverage (Coca-Cola®).
- ^j Dose administration of omeprazole is to occur during the mornings of Days 4 through 9 following an overnight fast of at least 10 hours.
- k Blood samples for determination of sotorasib plasma concentrations and PK parameters will be collected: Predose (Hour 0), 0.5, 1, 1.5, 2, 3, 4, 6, 8, 10, 12, 24, 36, and 48 hours postdose following administration of sotorasib on Days 1 and 9. The PK sample collected 30 minutes postdose will have a sampling window of ± 2 minutes, samples collected from 1 through 3 hours postdose will have a sampling window of ± 5 minutes, samples collected from 4 through 10 hours postdose will have a sampling window of ± 10 minutes, and samples collected from 12 through 48 hours postdose will have a sampling window of ± 20 minutes. Times of all PK samples will be recorded to the nearest minute.
- ¹ Adverse events will be recorded from initiation of study treatment on Day 1 until EOS or ET. Serious adverse events will be recorded from the time the subject signs the Informed Consent Form through 30 days after the last dose of study treatment or until EOS or ET (whichever is later).

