8.5.3. Pharmacokinetic Statistical Methodology

A statistical analysis will be conducted to investigate the drug-drug interaction, the primary PK parameters will be AUC_{inf} , $AUC_{0-t_{last}}$, and C_{max} for sotorasib on each of the dosing days. All other PK parameters will be regarded as secondary and will not be subject to inferential statistical analysis.

A linear mixed effects model will be used to analyze log-transformed primary PK parameters. The model will assume fixed effect for treatment and a random effect for subject. Geometric mean ratios for C_{max} and AUC values and associated 90% confidence intervals (Test/Reference) will be estimated. The “Reference” treatment for PK analysis will be sotorasib administered alone with water, while the “Test” treatment will be omeprazole administered in combination with sotorasib and an acidic beverage.

For each PK parameter separately, the least squares mean (LSM) for each treatment, difference in LSMS between the test and reference treatments, and corresponding 90% confidence interval (CI) will be calculated; these values will then be back-transformed to give the geometric least squares mean (GLSM), ratio of GLSMs, and corresponding 90% CI.

Additionally, the pooled estimate (across all treatments) of the within-subject CV will be calculated, and residual plots will be produced to assess the adequacy of the model(s) fitted.

Examples of the SAS code that will be used are as follows:

Mixed Model Analysis

```
proc mixed data = <data in>;
  by parcatln parcat1 pkday paramn param;
  class trtan usubjid;
  model l_pk = trtan aperiod trtseqp / cl residual ddfm = kr;
  lsmeans trtan / cl pdiff = control('1') alpha = 0.1;
  random intercept / subject = usubjid(trtseqp);
  ods output lsmeans = <data out>;
  ods output diffs = <data out>;
  ods output covparms = <data out>;
run;
```

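### The linear trapezoidal rule across 12-hour sampling gaps overstates each period's AUC by about 3-5% under a one-compartment model with the stated 5-hour half-life; the error largely cancels in the ratio and is cheap to reduce.

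*SAP*

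**What the plan says.** SAP 8.5.1 attaches this footnote to AUC from time zero to the last quantifiable concentration: "The AUC will be calculated using the linear trapezoidal (linear interpolation) rule". It gives no separate rule for the declining phase. AUCinf takes the same area up to tlast and adds a tail, footnoted "Based on the last observed quantifiable concentration".

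Protocol Appendix 8, footnote k, sets the samples on Days 1 and 9 at "Predose (Hour 0), 0.5, 1, 1.5, 2, 3, 4, 6, 8, 10, 12, 24, 36, and 48 hours postdose". The last three intervals (12-24, 24-36 and 36-48 h) are therefore each 12 hours wide.

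Protocol 1.2 states that "The sotorasib mean terminal elimination half-life is 5 hours", with a standard deviation of 2, and that "The median time of the maximum observed concentration (t_{max}) is 1 hour".

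AUClast and AUCinf are two of the three primary parameters. SAP 8.5.3 reports a geometric least squares mean for each treatment, and for the ratio the "associated 90% confidence intervals (Test/Reference) will be estimated".

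**The concern.** Between two points on an exponential decline, a straight line lies above the curve, and the excess grows with the width of the gap in half-lives. Here the gaps are 12 / 5 = 2.4 half-lives. The plan itself expects a log-linear terminal decline when it fits the elimination rate constant (SAP 8.5.1.1), so a straight line is a poor approximation in just the region where samples are sparse.

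What is at stake is the accuracy of the AUCs and geometric least squares means reported for each treatment, and of CL/F and Vz/F, which are derived from AUCinf. The Test/Reference ratio is affected only to the extent that the error differs between Day 1 and Day 9.

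**Working it through.** The documents give no figure for integration error, so there is nothing of the plan's to reproduce. The check compares the rule at the nominal sampling times with the exact integral.

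**Inputs from the documents.** Sampling times (Protocol Appendix 8); half-life 5 h, SD 2 h, so 3-7 h was examined; reference tmax 1 h (Protocol 1.2).

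**Assumptions.** One compartment with first-order absorption; Day 9 tmax of 1.5-4 h; tlast of 24-48 h. The documents give none of these. Protocol 1.2 allows a rough check on shape: 0.693 x 211 L / 26.2 L/h = 5.6 h. That fits a single-exponential decline, but the two inputs have CVs of 135% and 76%.

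**Step 1: one 12-hour gap.** With x = 12 ln2 / half-life, linear area / true area = (x/2)(1 + e^-x) / (1 - e^-x).
- 5 h: x = 1.664, e^-x = 0.1895; 0.832 x 1.1895 / 0.8105 = 1.22
- 3 h: x = 2.773, e^-x = 0.0625; 1.386 x 1.0625 / 0.9375 = 1.57
- 7 h: x = 1.188, e^-x = 0.3048; 0.594 x 1.3048 / 0.6952 = 1.11

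**Step 2: whole profile, half-life 5 h, tmax 1 h, tlast 48 h.** The error by segment, as a percentage of true AUClast, is -0.66 (0-12 h), +3.54 (12-24 h), +0.67 (24-36 h) and +0.13 (36-48 h). The sum is +3.68%. The 12-24 h gap supplies nearly all of it. AUCinf gives +3.7%. With tlast 24 h, AUClast is +3.0% and AUCinf +2.9%.

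**Step 3: slower absorption and the alternative rule** (half-life 5 h, tlast 48 h, AUClast; the ratio factor is relative to a reference tmax of 1 h).

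| tmax (h) | Linear error | Linear-up/log-down error | Ratio factor, linear | Ratio factor, log-down |
|---|---|---|---|---|
| 1 | +3.7% | -1.0% | 1 | 1 |
| 1.5 | +4.2% | -0.6% | 1.005 | 1.004 |
| 2 | +4.5% | -0.5% | 1.008 | 1.005 |
| 3 | +5.0% | -0.5% | 1.012 | 1.005 |
| 4 | +5.4% | -0.7% | 1.016 | 1.002 |

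**Step 4: wider range.** Over half-lives of 3-7 h, the linear error runs from +1.9% (7 h, tmax 1 h, tlast 24 h, AUCinf) to +6.8% (3 h, tmax 4 h, tlast 48 h), and the ratio factor from 1.003 to 1.034. A bi-exponential decline with a 5 h terminal half-life gives about +1.7 to +3.5% when tmax is near 1 h, and -0.9 to +5.1% over all cases run.

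**Step 5: is the direction of the ratio shift fixed?** No (half-life 5 h, reference tmax 1 h and tlast 48 h).
- Day 9 tlast 24 h, AUClast: 0.993 at the same tmax, 1.001 at tmax 2 h.
- Day 9 tlast 24 h, AUCinf: 0.997, 0.999 and 1.003 at tmax 1.5, 2 and 3 h.
- A pure 2 h lag on Day 9: 0.990 with the linear rule, 0.975 with log-down.

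The 12-hour gaps are also not the only source. For tmax 1 h against 2 h, the linear error rises by 4.48 - 3.68 = 0.80 points. Of this, -0.21 - (-0.66) = 0.45 points arise before 12 h, from sampling around the peak.

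**Step 6: derived parameters.** CL/F is dose / AUCinf, so an AUCinf 3.7% too high makes CL/F 1 - 1/1.037 = 3.6% too low. Vz/F follows CL/F.

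**The case against.** The linear rule is prespecified, simple and applied identically to both periods. The primary comparison is within subject, so most of the error cancels. The earlier omeprazole studies gave AUCinf ratios of 0.582 (fasted) and 0.430 (fed) per Protocol 1.3. Against those, a shift of at most 1.6% at the stated half-life is trivial: 0.582 x 1.016 = 0.591. No equivalence limits are stated that so small a shift could cross. Interpolating between observed points and extrapolating a tail are separate choices, so pairing a linear rule with a log-linear tail is not a contradiction. Changing the rule could also weaken comparability with earlier studies, whose AUC method these documents do not give. All of this stands.

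The alternative has limits too. It is biased slightly downward (about -0.4 to -1.4% for AUClast over half-lives of 3-7 h), it only partly removes the ratio shift when the tmax delay is small, and with a 2 h lag it moves the ratio further from 1 than the linear rule does.

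A reader might infer that the rule tilts the study toward finding that the beverage restores exposure. The documents do not support that. Nowhere do they say that absorption is slower on Day 9, and Step 5 shows that a lag or an earlier Day 9 tlast can cancel or reverse the shift. An earlier tlast is plausible if Day 9 exposure is lower.

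What the objection does not remove is the per-period error. It needs no assumption about Day 9, and it does not cancel in the AUCs, geometric least squares means, CL/F or Vz/F reported for each treatment.

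**Conclusion.** The point holds as a small gain in accuracy. At the documents' own half-life and tmax, a one-compartment profile gives per-period AUCs about 3-4% too high, rising to about 5% with slower absorption. A 6-7% error needs a half-life near 3 h together with a tmax of 3 h or more. The true size depends on the profile shape, which the documents do not give.

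The effect on the Test/Reference ratio is about +0.5 to +1.6% if Day 9 tmax is delayed to 1.5-4 h with the same half-life and tlast. It has no fixed direction otherwise and is too small to change what the study concludes about the interaction. This is an inexpensive improvement to make; the primary comparison remains valid without it.

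**What to change.** In SAP 8.5.1, footnote b, specify the linear-up/log-down trapezoidal rule for AUClast and AUCinf. Report the linear-rule AUCs and ratios as a sensitivity line, so that results can be set beside the earlier omeprazole studies. If programming has already begun, the minimum is to add linear-up/log-down as a supplementary analysis identified in the clinical study report, which SAP Section 1 allows.

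The cost is one footnote, one software setting and one extra set of table rows; no further samples or subjects are needed. The downside is that AUC values may differ by a few percent from earlier studies if those used the linear rule, which the sensitivity line would show.
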